### 8.10.2 PSA

As long as patient safety is the primary concern, in the absence of other indicators of disease progression, therapy should not be discontinued solely on the basis of a rise in PSA. PSA progression is defined as the date that a 25% or greater increase and an absolute increase of 2.0 ng/mL or more from the nadir is documented and confirmed by a second value obtained 3 or more weeks later. Where no decline from baseline is documented, PSA progression is defined as a 25% increase from the baseline value along with an increase in absolute value of 2.0 ng/mL or more after 8 weeks.

### 8.10.3 Bone

Record post-treatment changes as either “no new lesions” or “new lesions.”

In the absence of clearly worsening soft-tissue (nodal and visceral) disease or disease-related symptoms, progression at the first scheduled assessment should be confirmed on a second scan performed 6 or more weeks later. In the rare case where visible lesions disappear, this too should be confirmed.

Progressing disease on bone scan is considered when at least 2 new lesions are observed. Yet, progression remains unconfirmed unless at least 2 *additional* new lesions appear at a subsequent time point.

Unless clinically indicated, there is no need to perform a follow-up bone scan before 12 weeks of treatment. To define disease progression requires a confirmatory scan (which shows additional new lesions compared with the first follow-up scan) performed 6 or more weeks later. When further progression is documented on the confirmatory scan, the date of progression recorded for the trial is the date of the first scan that shows the change.

#### 8.10.4 Nontarget lesions

When assessing nontarget lesions, the definitions in Table 2 will apply. The overall assessment of preexisting plus new lesions at the first time point must show unequivocal progression. Progression at the first time point remains unconfirmed unless progression is confirmed to the same or greater extent at a subsequent time point.

*Table 2. RECIST response criteria for nontarget lesions*

Response	Evaluation of Nontarget Lesions
Complete response (CR)	the disappearance of all nontarget lesions and normalization of tumor marker levels
Incomplete response/ stable disease (SD)	the persistence of one or more nontarget lesions and/or maintenance of tumor marker levels above the normal limits
Progressive disease (PD)	the appearance of one or more new lesions and/or unequivocal progression of existing nontarget lesions

#### 8.10.5 Patient-reported outcomes

FACT-P scores will be collected and described over time for this study to assess quality of life changes. No formal statistics will be applied to this exploratory endpoint.

Transient increases in pain may occur before improvement, and those occurring in the first 12 weeks should not affect the course of treatment in the absence of other compelling evidence of disease progression. Changes in symptoms should be confirmed as for other outcome measures. Monitor other domains that may help determine whether the disease is progressing, including worsening in global quality of life, developing urinary or bowel compromise, or needing to change anticancer therapy.

### 8.10.6 Evaluating best overall response

The best overall response is the best response recorded from the start of treatment until either disease progression or recurrence. The investigator's determination of best overall response will be based both on response criteria and on confirmation criteria. To be assigned a status of confirmed partial response or complete response, changes in tumor measurements must be confirmed by repeat assessment performed at least 4 weeks after the criteria for response are first met. To confirm stable disease, follow-up measurements must meet SD criteria at a minimum interval of 4 weeks after SD was first documented. Table 3 can be used as an assessment tool.

**Note:** If unconfirmed progression noted at the first time point is not confirmed at a second time point, the next assessment time point after the first that meets the criteria for progression will be treated as time point 1.

*Table 3. Assessing Overall Response*

Target Lesions	Nontarget Lesions	New Lesions	Overall Response
CR	CR	No	CR
CR	Incomplete response/SD	No	PR
PR	Non-PD	No	PR
SD	Non-PD	No	SD
PD	Any	Yes or No	PD
Any	PD	Yes or No	PD
Any	Any	Yes	PD

Abbreviations: CR, complete response; PD, progressive disease; PR, partial response; SD, stable disease.

Subjects with global deterioration of health status who require treatment to be discontinued without objective evidence of disease progression should be classified as having symptomatic deterioration. Every effort should be made to document their objective progression, even after discontinuing treatment.

Subjects who do not have tumor response assessment due to rapid progression or toxicity will be considered nonresponders, will be included in the denominator for the response rate, and will be classified into one of the categories listed below:

- death attributed to disease progression
- early discontinuation attributed to disease progression
- death attributed to drug toxicity
- early discontinuation attributed to drug toxicity

**Note:** If a subject receives subsequent therapy before tumor progression is documented, the reason for changing therapy must be reported. Reasons include clinical progression, drug toxicity, or secondary therapy for maintaining tumor response.

For immunotherapies, atypical patterns of response, including delayed responses, new lesions with mixed patterns of response, pseudoprogression due to immune infiltration (transient), and prolonged stable or partially responsive disease. In this study, we will describe the immune-

modified responses using the following **table 4** PCWG3-modified RECIST 1.1 and immune-modified response and progression will be reported separately in this study.

Derivation of overall immune-related response for all assessed time points			
Measurable response	Nonmeasurable response		Overall response
Index and new measurable lesions (total measurable tumor burden)†	Non-index lesions	New nonmeasurable lesions	Using irRC
100% decrease	Absent	Absent	irCR‡
≥50% decrease	Any	Any	irPR‡
<50% decrease to <25% increase	Any	Any	irSD
≥25% increase	Any	Any	irPD‡

\* After Wolchok et al. (43). irCR = immune-related complete response—complete disappearance of all index and new measurable lesions; irPR = immune-related partial response—decrease in tumor volume ≥50% relative to baseline; irSD = immune-related stable disease—not meeting criteria for irCR or irPR, in absence of irPD; irPD = immune-related progressive disease—increase in tumor volume ≥25% relative to nadir.

† Index and non-index lesions are selected at baseline. Index lesions are measurable (>5 × 5 mm), and non-index lesions are not measurable (<5 × 5 mm, ascites, bone lesions, etc.). Changes are assessed relative to baseline and include measurable lesions only (>5 × 5 mm).

‡ Assuming response and progression are confirmed by a second assessment at least 4 weeks apart.

Table 4. Immune modified RECIST criteria.

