### 4.2 Secondary Endpoints

1. To describe the efficacy of PD-L1 inhibition with avelumab as measured by PCWG3 using RECIST1.1
2. To describe the radiographic progression free survival (rPFS) of PD-L1 inhibition with avelumab using modified PCWG3 with both RECIST 1.1 and iRECIST criteria in this setting.
3. To describe the overall survival of PD-L1 inhibition in this setting.
4. To described the toxicities and safety of PD-L1 inhibition with avelumab in men with metastatic neuroendocrine-like prostate cancer.

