### 8.11.3 Progression-free survival

Progression-free survival (PFS) is a composite endpoint defined as the time from study entry or random assignment to radiographic disease progression in bone or soft-tissue, symptoms (clinical deterioration), or death. PSA changes will not be used to define PFS in this study. A PFS estimate using both conventional PCWG3-modified RECIST 1.1 criteria and immune-modified RECIST criteria (Table 4) will be reported. Use an interval-censored approach in which all assessments of the composite PFS endpoint (i.e. bone, CT scans, and symptom assessments) are performed at the same time points. All assessments of disease should be collected at the same time interval every 8 weeks.

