## 11.6 Secondary Objectives

1. To describe the efficacy of PD-L1 inhibition with avelumab as measured by PCWG3 using RECIST1.1
2. To describe the radiographic progression free survival (rPFS) of PD-L1 inhibition with avelumab using immune modified and PCWG3-modified RECIST 1.1 criteria in this setting.
3. To describe the overall survival of PD-L1 inhibition in this setting.
4. To described the toxicities and safety of PD-L1 inhibition with avelumab in men with metastatic neuroendocrine-like prostate cancer.

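### The immune rPFS is named as iRECIST but defined by Table 4, which is irRC; for the primary iRECIST response, the passages on unconfirmed progression are not reconciled

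*Combined protocol and SAP*

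**What the plan says.** **Immune rPFS.** Secondary objective 2 in section 4.2, and likewise in the synopsis, asks for rPFS "using modified PCWG3 with both RECIST 1.1 and iRECIST criteria in this setting". Section 8.10 describes iRECIST as RECIST 1.1 principles plus confirmation of progression, with a reset if shrinkage follows instead. Section 8.11.3 then says: "A PFS estimate using both conventional PCWG3-modified RECIST 1.1 criteria and immune-modified RECIST criteria (Table 4) will be reported". Section 11.6 rewords the objective as "using immune modified and PCWG3-modified RECIST 1.1 criteria in this setting", which does not settle which immune criterion is meant.

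Table 4, in section 8.10.6, is captioned as immune-modified RECIST, but its overall-response column is headed as irRC. Its footnotes read "irPD = immune-related progressive disease—increase in tumor volume ≥25% relative to nadir" and "irPR = immune-related partial response—decrease in tumor volume ≥50% relative to baseline", with index lesions larger than 5 × 5 mm. The sentence that introduces the table also applies it to immune-modified responses.

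**Measurement.** Sections 8.9.9 and 8.9.12 provide for sums of longest diameters only. Table 1 sets PR at a decrease of at least 30% from the baseline LD sum. It sets PD at an increase of at least 20% from the smallest LD sum, or a new lesion.

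**Primary response.** The synopsis and sections 4.1, 8.10 and 11.5 all name iRECIST. Section 8.10.6 ends the best-response window at disease progression, without saying whether it must be confirmed, and the last row of Table 3 turns any new lesion into an overall PD. Section 8.9.12 says that a new lesion alone is not confirmed PD, and the Note in 8.10.6 restarts the count when a first progression is not confirmed.

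**The concern.** An analyst who follows section 8.11.3 would report an irRC-based PFS under an objective that names iRECIST. The two differ in threshold, in the quantity measured and in how new lesions enter. Both require confirmation, but Table 4 asks for at least 4 weeks where section 8.9.12 asks for at least 6. Table 4 also puts a 50% response threshold beside the 30% rule of Table 1, with nothing to say which one governs immune response.

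For the primary endpoint, confirmation with reset is what section 8.10 gives as the difference between iRECIST and RECIST 1.1. If the best-response window were closed at a first, unconfirmed PD, that difference would be lost, and the primary count would move towards secondary objective 1: "To describe the efficacy of PD-L1 inhibition with avelumab as measured by PCWG3 using RECIST1.1". The decision rests on small counts, at least 2 responders of 18 and at least 5 of 44, so the classification of a single man can matter.

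**Working it through.** **1. The plan's own design figures.** Section 11.1 gives n1 = 18, stop at 1 or fewer responses, 44 in total, success at 5 or more, p0 = 5% and p1 = 20%. With X1 ~ Bin(18, p) and X2 ~ Bin(26, p):

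- P(stop | 5%) = 0.95^18 + 18 × 0.05 × 0.95^17 = 0.3972 + 0.3763 = 0.7735 (stated 0.77).
- P(success) = sum over x = 2 to 18 of P(X1 = x) × P(X2 ≥ 5 − x). This is 0.0495 at p = 5% (stated 0.05) and 0.8806 at p = 20% (stated 88%).
- 44 / 0.9 = 48.9, so 49 (stated 49).

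All of these reproduce. The issue is one of endpoint definition, not design arithmetic.

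**2. Table 4 thresholds on the diameter scale.** Assumption: all lesions change in the same proportion and no new lesion appears. The footnotes say volume, while the 5 × 5 mm lesion size suggests a two-dimensional measure.

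| Reading | irPD, +25% | irPR, −50% |
|---|---|---|
| Area | 1.25^(1/2) − 1 = +11.8% | 1 − 0.5^(1/2) = 29.3% decrease |
| Volume | 1.25^(1/3) − 1 = +7.7% | 1 − 0.5^(1/3) = 20.6% decrease |
| LD sum | +25% | 50% decrease |
| *Table 1, for comparison* | *+20%* | *30% decrease* |

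For response, the gap is negligible if area is meant (29.3% against 30%). For progression, there is a gap on every reading.

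**3. The direction is not fixed.** Growth of 12% in diameter from nadir gives 1.12² − 1 = +25.4% in area and 1.12³ − 1 = +40.5% in volume. That is irPD on either reading, but below the 20% of Table 1. Growth of 22% is PD in Table 1, but irSD if Table 4 is applied to the LD sum (22% < 25%). In addition, Table 4 adds new measurable lesions to the total burden, whereas Table 1 makes a new lesion PD by itself. The net effect on rPFS cannot be derived from the documents.

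**4. Primary response, two illustrative cases.**

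- Target LD sum +22% at week 8, then −35% from baseline at weeks 16 and 24. Under the reset in section 8.10 this is a PR, and it is confirmed because the two scans are 8 weeks apart (at least 4 are required). If the window in 8.10.6 closes at the week 8 PD, the man is a nonresponder.
- Target LD sum −35% on two scans, with one new lesion at the first. Section 8.9.12 does not accept the new lesion alone as confirmed progression. Table 3 offers only PD and has no entry for a target PR with an unconfirmed new lesion.

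**5. Confirmation interval.** Imaging is every 8 weeks, with a window of 7 days either way. The shortest gap between consecutive scheduled scans is 56 − 7 − 7 = 42 days, or 6 weeks. Scheduled scans therefore always meet the 6 weeks of sections 8.9.12 and 8.10.3. The 4 weeks of section 8.11.1 makes a difference for progression only with unscheduled scans.

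**The case against.** The strongest reply is that the immune rPFS is a descriptive secondary endpoint, estimated by Kaplan-Meier with no test or decision attached, and that the primary rule is nearly settled by the text. Both parts have weight. A reset that recognises later shrinkage makes little sense if the response window has already closed. Section 8.10.6 bases best response on confirmation criteria as well as response criteria, and its Note points the same way. It can also be said that the first case in step 4 needs treatment and imaging to continue after week 8. Section 8.5 stops treatment at progression, but the synopsis and schedule footnote 3 permit treatment beyond radiologic progression, so such a case can arise. What remains is one unqualified term in 8.10.6 and a Table 3 that is not tied to either criterion.

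A reader might infer more than the documents support:

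- **That Table 4 contradicts itself**, because another footnote says "Changes are assessed relative to baseline and include measurable lesions only". With a burden of 100 at baseline, 50 at nadir and 70 now, the change is 70/50 − 1 = +40% from nadir and 70/100 − 1 = −30% from baseline. But irPD is defined from nadir and irSD only when irPD is absent, so the case is irPD. The general footnote is loose, not decisive.
- **That bone progression would never count.** This follows only if Table 4 is read alone. Section 8.11.3 counts "radiographic disease progression in bone or soft-tissue, symptoms (clinical deterioration), or death", and section 8.10.3 has its own bone rule.
- **That Table 5 or section 11.5.1 excludes such responders.** A responder falls in category 1 or 2, so calling category 4 a treatment failure does not say when the window closes. Section 11.5.1 sits under 11.5, which names iRECIST.
- **That the stated power or type I error is wrong.** Suppose the true rate is 20% and a share f of responders qualify only after unconfirmed progression and are not counted. The effective rate is then 0.20 × (1 − f), and power is 0.824 at f = 10% and 0.745 at f = 20%. Conversely, if counting such responses added 0.5 to 2 points to the 5% null, the rejection probability would be 0.069 to 0.145. The documents give neither quantity, and their text favours counting, so these figures are conditional illustrations only.

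**Conclusion.** The mismatch for the immune rPFS is clear on the text: iRECIST is named, irRC is specified, and Table 4's quantity is not one that the plan collects. On the diameter scale, the progression threshold is +7.7%, +11.8% or +25% depending on the reading, against +20% in Table 1. These figures assume uniform change and no new lesions. The number of men affected and the net direction are unknown.

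For the primary response the point is narrower. The plan leans towards counting a CR or PR after unconfirmed progression, but no sentence says so, and section 8.10.6 with Table 3 is not reconciled with sections 8.9.12 and 8.10. The stated operating characteristics stand. This should be fixed before analysis; because the firm error lies in a descriptive secondary endpoint, it does not rank as a fatal flaw.

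**What to change.** These changes concern endpoint classification only.

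1. In section 8.11.3, replace the reference to Table 4 with iRECIST confirmed progression as described in 8.10, with bone progression by 8.10.3. Align objective 2 in section 11.6 with 4.2.
2. Delete Table 4, or keep it only as a supplementary description labelled irRC, used for neither the primary response nor the rPFS. Change the sentence that introduces it accordingly.
3. In section 8.10.6, insert the word confirmed before disease progression for the iRECIST analysis. State that a confirmed CR or PR after unconfirmed progression counts, with PR by the 30% LD-sum rule of Table 1.
4. Label PD in Tables 1 to 3 as RECIST 1.1 PD for the secondary analysis, and as unconfirmed progression for the iRECIST analysis until it is confirmed. State in Table 3 how a target PR with an unconfirmed new lesion is classified.
5. Use the 6-week interval of sections 8.9.12 and 8.10.3 to confirm progression and the 4-week interval of 8.10.6 to confirm response, and bring 8.11.1 into line.

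The cost is protocol and SAP wording. Target LD sums, new-lesion diameters, bone scans and 8-weekly imaging are already planned, and no area or volume measurement is needed for the primary response or the rPFS.

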## 8.11 Confirmatory Measures/Duration of Response

### 8.11.1 Confirming time-to-event outcomes

Any post-treatment change in disease status (imaging, biomarker studies), be it favorable or unfavorable, should be confirmed using a second assessment at a later time point 4 or more weeks later. Unconfirmed results will be reported as such.

### 8.11.2 Duration of overall response

Duration of overall response is measured from the time when partial response or complete response is first noted until the date when recurrent or progressive disease is objectively documented. Duration of overall complete response is measured from the time the criteria for complete response are first met until the first date that recurrent disease is objectively documented. Duration of stable disease is measured from the start of treatment until the criteria for progression are met.

### 8.11.3 Progression-free survival

Progression-free survival (PFS) is a composite endpoint defined as the time from study entry or random assignment to radiographic disease progression in bone or soft-tissue, symptoms (clinical deterioration), or death. PSA changes will not be used to define PFS in this study. A PFS estimate using both conventional PCWG3-modified RECIST 1.1 criteria and immune-modified RECIST criteria (Table 4) will be reported. Use an interval-censored approach in which all assessments of the composite PFS endpoint (i.e. bone, CT scans, and symptom assessments) are performed at the same time points. All assessments of disease should be collected at the same time interval every 8 weeks.

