### 11.6.1 Key Secondary Objectives – analysis plan

The Kaplan-Meier method will be used to estimate both forms of progression-free survival as well as the overall survival distributions. Summary statistic will be computed for the duration of time on treatment distribution. The correlative science analyses will be considered exploratory and interpreted as such and reported using descriptive statistics and associations with clinical outcomes including response (radiographic) and progression free and overall survival.

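### Radiographic PFS is a secondary endpoint, but the plan's only PFS definition also counts clinical deterioration as an event

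*Combined protocol and SAP*

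**What the plan says.** The synopsis and Section 4.2 give the second secondary objective as "To describe the radiographic progression free survival (rPFS) of PD-L1 inhibition with avelumab using modified PCWG3 with both RECIST 1.1 and iRECIST criteria". The statistics chapter repeats it in Section 11.6 as "radiographic progression free survival (rPFS) of PD-L1 inhibition with avelumab using immune modified and PCWG3-modified RECIST 1.1 criteria". Neither place says what counts as an event, when the clock starts, or when a subject is censored.

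Section 8.11.3 is the only text that defines a PFS event. It gives the "time from study entry or random assignment to radiographic disease progression in bone or soft-tissue, symptoms (clinical deterioration), or death", excludes PSA changes, and says that estimates under both the conventional and the immune-modified criteria will be reported. It then confirms that symptoms belong to the endpoint by asking that "all assessments of the composite PFS endpoint (i.e. bone, CT scans, and symptom assessments) are performed at the same time points".

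Section 11.6.1 supplies the method: "The Kaplan-Meier method will be used to estimate both forms of progression-free survival as well as the overall survival distributions". It removes no symptom events.

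Section 8.10.6 says that subjects who must stop treatment because their general health has worsened "without objective evidence of disease progression should be classified as having symptomatic deterioration". It adds: "Every effort should be made to document their objective progression, even after discontinuing treatment".

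**The concern.** The objective names one endpoint and the definition describes another. A subject who stops treatment for clinical deterioration with no imaging progression is an event under Section 8.11.3. Under Section 8.10.6 the same subject has not yet progressed objectively and should still be assessed for it.

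The trial is open-label and single-arm, and clinical deterioration rests largely on the investigator's judgement. Counting it makes an estimate labelled radiographic partly a clinical one. That estimate will be read against radiographic PFS elsewhere, where a shorter composite could make the drug look worse. The synopsis hypothesis also names prolonged PFS in some men among the grounds for further study, although it sets no PFS threshold.

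**Working it through.** **Figures in the plan.** The plan states no figure for rPFS, so there is none to reproduce. Its only sizing is the Simon design for response (Section 11.1): stop with 1 or fewer responses in 18, and declare activity with 5 or more in 44. Exact binomial calculation gives an early termination probability of 0.7735 at a 5% response rate (stated 0.77), a type I error of 0.0495 (stated 0.05) and power of 0.8806 at 20% (stated 88%). Allowing for unevaluable subjects, 44 / 0.90 = 48.9, that is 49 (stated 49). None of these depends on the PFS definition.

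**The passages side by side.**

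| Question | Synopsis, 4.2, 11.6 | 8.11.3 | 8.10.6 | 11.6.1 |
|---|---|---|---|---|
| Endpoint named | rPFS | PFS | not applicable | PFS, both forms |
| Is deterioration without imaging progression an event? | not stated; the name implies no | yes | not objective progression | not stated |

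The two forms in Section 11.6.1 are the two sets of response criteria, as in Section 8.11.3. They are not a radiographic and a symptom-inclusive version. No other section defines rPFS.

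**Direction.** Let R be the time to radiographic progression or death, and C the time to clinical deterioration. The Section 8.11.3 event time is min(R, C), which never exceeds R. Its underlying median therefore cannot exceed the median of R.

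**Size, under assumptions.** The document gives no share of symptom-only events. Assume constant, independent hazards a (radiographic progression or death) and b (deterioration), and let s = b / (a + b) be the share of first events that are deterioration alone.

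- Composite median = ln 2 / (a + b)
- rPFS median = ln 2 / a
- Ratio of rPFS to composite = (a + b) / a = 1 / (1 − s)

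| Assumed s | Ratio 1 / (1 − s) | Composite median if the rPFS median were 3.8 months | Symptom-only events if all 44 subjects have an event |
|---|---|---|---|
| 10% | 1.11 | 3.8 × 0.90 = 3.42 | 4.4 |
| 20% | 1.25 | 3.8 × 0.80 = 3.04 | 8.8 |
| 30% | 1.43 | 3.8 × 0.70 = 2.66 | 13.2 |

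The 3.8 months is only a scale. Section 3.1 quotes it as the shorter of two PFS figures from a chemotherapy trial in men with NEPC. Simulation with that median gives composite medians of 3.41 months at s = 10% and 3.04 months at s = 20%, which agrees with the formula.

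**The case against.** **Section 8.11.3 is headed PFS, not rPFS, so it may define something else.** It never uses the term rPFS, and the objective says radiographic wherever it appears. However, Section 8.11.3 promises estimates under the same pairing of conventional and immune criteria as the objective, and Section 11.6.1 analyses no other PFS. If it is nonetheless a separate endpoint, rPFS has no definition at all. Either way the text needs repair. What stands is that the mismatch bites only if the analysts follow Section 8.11.3 as written.

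**Deterioration is not without criteria.** A reader might infer that it is wholly unconstrained. Section 8.10.6 ties it to worsening that requires treatment to stop, and Section 8.10.5 asks that symptom changes be confirmed and discounts early increases in pain. Judgement remains, but within some limits.

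**The ratios lean high.** This stands. Men who deteriorate clinically are plausibly close to imaging progression or death, which would bring the ratio nearer 1. Scans every 8 weeks also make progression times uneven, so a smooth proportional shift is only a guide.

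**The contrast between the two criteria is not seriously blurred.** A reader might infer that shared symptom events spoil it. But no formal comparison is planned, and deaths are common to both criteria under any definition.

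**Dropping symptom events has a price.** This also stands. Note 10 to the Section 8 schedule continues radiographic follow-up only until other treatment starts, and where available. Censoring at that point may be informative and could bias rPFS upwards.

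**Conclusion.** The mismatch is real. Followed as written, the plan reports a composite clinical and radiographic PFS under an rPFS objective. The underlying composite median is no longer than that for radiographic progression or death. The ratio of 1.11 to 1.43 rests on an assumed 10% to 30% symptom-only share and on constant, independent hazards. It illustrates the possible effect and does not predict it.

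Two stronger readings are not supported. First, a reader might infer that the time origin also makes the endpoint non-radiographic. It does not. Section 5.8 says the trial is not randomised, so the mention of random assignment has no effect, and an origin cannot change which events count. What remains is a tidy-up: study entry is undefined, Section 5.1 follows subjects from registration, and the synopsis and Section 8.6.3 follow them from enrolment. Second, a reader might infer that the trial's decision is at risk. rPFS is descriptive and unpowered, and the response endpoint, sample size and error rates do not depend on it.

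**What to change.** In Sections 8.11.3 and 11.6.1:

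1. Define rPFS, separately under each response criterion, as time from one stated origin (for example enrolment, used throughout) to first radiographic progression in bone or soft tissue or death from any cause. Name the criteria identically in Sections 4.2, 8.11.3 and 11.6. At present Section 4.2 says iRECIST, while Section 8.11.3 points to Table 4, which carries irRC thresholds.
2. State that clinical deterioration without imaging progression is not an rPFS event, and that such subjects stay at risk while imaging continues.
3. State that subjects who start new therapy before imaging progression are censored at their last adequate scan.
4. Report the Section 8.11.3 composite as a separately labelled, symptom-inclusive PFS. It also serves as a sensitivity analysis for informative censoring.

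As tidy-up only, delete the reference to random assignment and reconcile the registration and enrolment origins.

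The cost is a wording change and one additional symptom-inclusive Kaplan-Meier estimate alongside rPFS. Section 8.6.1 and note 10 to the Section 8 schedule already provide for scans after treatment stops for reasons other than progression, so no new assessments are needed. The downside is some possibly informative censoring, which the composite estimate would help to show.
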